Similar to the above, any participants who select a less healthy item (D/E) as part of their meal will be coded as 1, and participants who have only selected options with a A/B/C value will be coded as 0. We will conduct a logistic regression to test whether NS labelling (Y/N) is associated with the likelihood of selecting a less healthy item.

Energy and nutrient content consumed at lunch

Similar to primary analyses, we will explore the impact of NS labelling on total energy and nutrient content of food consumed (linear outcome variables) through n=8 linear mixed models. The nutrients explored will be salt, sugar, fat, saturated fat, protein, fibre and fruit vegetable and nut content.

Transformations: N/A

Inference criteria: Results for primary analyses will be considered significant at p<0.05, and to account for multiple comparisons, secondary analyses will be considered significant at p<0.01.

Data exclusion: If participants leave the restaurant study session without ordering food their data will be excluded from analyses.

Missing data: If participants do not complete the dietary recall survey, and therefore do not provide data of later intake, then we will impute the missing data for this variable. Any missing data for other outcomes (e.g., PME) will also be imputed. We will complete multiple imputation with 5 imputed datasets(50) in R using the 'mice' package. Imputation will be reported in line with published guidance(51).

Exploratory analysis:

Other:

Sample size:

We conducted a simulation to estimate sample size required for two primary outcomes: PME and NPM scores. Our simulation was based on previous research and knowledge of the outlets confirmed for data collection.

We simulated running the study with 20 participants a day for 20 days (400 total data points). For PME, we estimated from previous research that we may have an intercept PME value of 1.85 (SD: 1.08), with an intervention effect of 1 (the intervention group will have PME values 1 unit greater than the control group on average, based on previous research(52)), and minimal difference in PME

scores between the two outlets (0.2). We also assumed ICC of approximately 0.200, and a standard deviation of the random intercept of eating group in a mixed model of 1. Across 200 simulations using a regression model clustered by day, we would have 94% power (95% CI 89.75, 96.86) to detect differences in PME between the two conditions.

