For NPM scores, we calculated using the two confirmed outlet menus, that we may have an intercept NPM score of -0.27 (SD: 3.29) with an intervention effect of 0.22 (the intervention group will select meals with with greater nutritional quality, shown by a 0.22 higher NPM score) based on previous research(26) and a mean difference between the two outlets of 1.4 (the difference in mean NPM scores for the two outlets). We also assumed ICC of approximately 0.819, and a standard deviation of the random intercept of eating group in a mixed model of 1. Across 200 simulations using a regression model clustered by day we would have 88.5% power (95% CI 83.25, 92.57) to detect differences in NPM scores between the two conditions.

Due to uncertainty over size of anticipated effects and available resources, we will increase the above desired maximum sample size (400) by 12.5% to 450 participants.

Stopping rule

Prior to the study we do not know with certainty what the rate of participant recruitment will be, and effect size estimates have a degree of uncertainty. To balance the trade-off between costs (e.g., in research time, participant burden) and likelihood of the study providing convincing evidence, we will conduct interim analyses to assess whether the results are convincing enough to conclude that effects on PME and nutritional quality of food order are present(53). The interim analyses will examine the effect sizes of these two primary outcomes and observed statistical significance. We will also calculate Bayes Factors to assess the strength of evidence for the experimental vs null hypotheses.

We will conduct the interim analysis when we have obtained approximately 50% of the full sample (224 participants, ~112 completers in each condition). If at this point, the data suggests that it is extremely unlikely that either of the predicted effects would be observed up to maximum sample size capacity (described above), and if Bayes Factors suggest there is evidence for the null hypothesis (BF10 < 0.3) then we will cease data collection and conduct full planned analyses.

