However, if the observed effect size suggests that an effect size statistically detectable at N=450 is present but is not statistically significant at interim, or Bayes Factors do not provide support for either the null or alternative hypothesis (BF10 > 0.3 and < 3), we will continue data collection to recruit the largest possible sample size and adjust p values (dividing by 2 for outcomes examined at interim to account for multiple analyses) to account for error rate inflation for final full sample analyses.

Due to the sample size required and potential difficulties in recruiting sufficient numbers for each stratum (e.g., lower SEP individuals, males) we may need to adjust plans during data collection. If we experience recruitment difficulty during the first month of data collection, we will prioritise stratifying by SEP ahead of age and sex, as individuals with a higher education level are more motivated by health when making food choices (16).

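### The interim look may support a success claim but has no significance level of its own, and only the final analysis is adjusted, so type I error control is not secured

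*Protocol*

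**What the plan says.** The Stopping rule section of the protocol gives the interim an efficacy purpose. It is to assess "whether the results are convincing enough to conclude that effects on PME and nutritional quality of food order are present". The tools are named: "The interim analyses will examine the effect sizes of these two primary outcomes and observed statistical significance", and "We will also calculate Bayes Factors to assess the strength of evidence for the experimental vs null hypotheses". The look comes at "approximately 50% of the full sample (224 participants, ~112 completers in each condition"), and the Sample size section sets the maximum: "we will increase the above desired maximum sample size (400) by 12.5% to 450 participants".

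Two decision rules follow.

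- **Stop for the null:** if an effect is extremely unlikely to be seen by the maximum sample size and BF10 is below 0.3.
- **Continue:** if an effect detectable at 450 "is present but is not statistically significant at interim", or if BF10 lies between 0.3 and 3. In that case p values for the outcomes examined at the interim are adjusted by a factor of 2, "to account for error rate inflation for final full sample analyses".

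No rule for stopping on success is written. The only level for the primary outcomes is under Inference criteria: "Results for primary analyses will be considered significant at p<0.05".

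**The concern.** The interim is a second opportunity to conclude that an effect exists. The protocol recognises that two looks inflate the error rate, but it corrects only the second. If the first look is read at the stated 5% level, the whole 5% is used at about half the sample, and any non-zero level at the final test takes the total above 5%.

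At stake is whether a success claim on either primary outcome at 224 participants has a known false-positive rate. A practical risk comes with it: while the boundary is unwritten, what counts as convincing can be settled after the interim data have been seen.

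**Working it through.** **Inputs.** Maximum sample 450 and interim at 224 (Sample size and Stopping rule). Level 0.05 (Inference criteria), taken as two-sided because the protocol does not say. BF10 limits 0.3 and 3 (Stopping rule). The protocol states no overall two-look error rate, so there is none to reproduce.

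**The protocol's own figures.** 400 × 1.125 = 450, as stated. Half of 450 is 225, against 224 stated, which agrees with its wording of approximately half. The information fraction is f = 224/450 = 0.498.

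**Two-look error per outcome.** With no true effect, the test statistics Z1 and Z2 are taken as bivariate normal with correlation √f = √0.498 = 0.706. The error is

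1 − P(|Z1| ≤ c1 and |Z2| ≤ c2),

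where c1 and c2 are the two-sided critical values: 1.960 for 0.05, 2.241 for 0.025, 2.178 for 0.0294, 2.807 for 0.005 and 1.977 for 0.048. The futility exit is ignored; it could only lower these figures.

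*Reading 1: interim p<0.05 is sufficient for a success claim.*

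| Interim level | Final level | Error per outcome |
|---|---|---|
| 0.05 | 0.025 | 6.4% |
| 0.05 | 0.05 | 8.3% |

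A simulation of 4 million draws with the interim at exactly half the sample also gave 6.4% for the first row.

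*Reading 2: the Bayes-factor rule is binding, so success at the interim needs p<0.05 and BF10 ≥ 3.* The protocol states no prior. As an assumption, take the default two-sided Cauchy prior for a two-sample t test with 112 per arm, independent observations, and scale from 0.2 to 1.0.

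| Prior scale | BF10 at p = 0.05 | Interim p at which BF10 = 3 | Error, final 0.025 | Error, final 0.05 |
|---|---|---|---|---|
| 0.2 | 1.58 | 0.0186 | 3.8% | 6.0% |
| 0.5 | 1.14 | 0.0146 | 3.5% | 5.7% |
| 0.707 | 0.90 | 0.0116 | 3.2% | 5.6% |
| 1.0 | 0.68 | 0.0087 | 3.0% | 5.4% |

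Under these priors p = 0.05 at the interim gives an inconclusive Bayes factor, so the rule sends the trial on, and the effective interim level falls to about 0.009 to 0.019. A directional or informed prior could put BF10 at 3 or more near p = 0.05, which would bring back Reading 1.

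**Thresholds that control both looks.** 0.0294 at each look gives 5.0%. 0.005 at the interim with 0.048 at the end gives 5.0%. 0.025 at each look gives 4.3%.

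**The case against.** The strongest objection is that the protocol never says p<0.05 alone is enough at the interim. The 0.05 level is given for the primary analyses and is not assigned to the interim. The continuation rule also keeps recruitment open while the Bayes factor is inconclusive. A reader might infer that a significant interim result is an automatic success exit, and hence that the error must exceed 5% even when the final level is correctly set. The documents do not support that: with a binding Bayes-factor rule, a default prior and a final level of 0.025, the error is 3.0% to 3.8%. This part of the objection stands.

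It does not clear the plan. Whether the Bayes factor must agree with the p value, which prior is used, and whether one or both outcomes must meet the criterion are all left open. Under the same priors, a final level of 0.05 still gives 5.4% to 6.0%.

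A second objection is that the protocol promises a full analysis plan before any interim analysis, and a numerical boundary could sit there. That is fair for the missing number. But the protocol does more than leave a gap: it states an adjustment and ties it to the final analysis alone, while giving the interim an efficacy purpose.

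A third is that larger error figures could be quoted. Literally halving the p values amounts to a final level of 0.10 and gives 12.5% per outcome. The chance of at least one false positive across two independent outcomes is about 12% at 0.05 and 0.025. The first comes mainly from the direction of the halving. The second comes mostly from having two primary outcomes, since 1 − 0.95² = 9.75% with no interim at all. Both are separate points and are not counted here.

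**Conclusion.** The point holds as an unsecured error rate, not as a proven breach. The interim can lead to a conclusion of efficacy, no interim level is stated, and the only adjustment is confined to the final analysis. With a final level of 0.025, the error per outcome is 6.4% if interim p<0.05 suffices, and about 3.0% to 3.8% if the Bayes-factor rule binds under a default prior. With a final level of 0.05, the corresponding figures are 8.3% and 5.4% to 6.0%.

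These figures assume two-sided tests, approximate normality, information proportional to the number of participants, and no credit for the futility exit. The Bayes-factor range also depends on the assumed prior and on treating observations as independent, although the trial randomises by day. The conclusion that control hinges on unstated choices does not depend on these details.

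**What to change.** Amend the Stopping rule before the interim, choosing one of two options.

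- **(a) Futility-only interim.** State that no success claim and no early stop for benefit will be made at the interim, and test each primary outcome at 0.05 at the end.
- **(b) Interim with a success option.** Set thresholds for the two looks that jointly give 5% per outcome, such as 0.0294 at each, or 0.005 at the interim and 0.048 at the end. Require the interim threshold for any success claim at that look, whatever the Bayes factor shows. State the BF10 prior, and say whether one or both primary outcomes must meet the criterion.

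Either option replaces the present factor-of-2 adjustment. The cost is protocol wording, plus a stricter interim success threshold under (b) or none under (a). Neither option deals with the multiplicity from having two primary outcomes, which needs its own decision.

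### The interim correction runs backwards: dividing the final p values by 2 and keeping p<0.05 tests both primary outcomes at p<0.10

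*Protocol*

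**What the plan says.** The Inference criteria set the level for the primary outcomes without qualification: "Results for primary analyses will be considered significant at p<0.05". The Sample size section names those outcomes: "We conducted a simulation to estimate sample size required for two primary outcomes: PME and NPM scores".

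The Stopping rule places an interim analysis at "approximately 50% of the full sample (224 participants, ~112 completers in each condition"), against a maximum of 450. Both primary outcomes are looked at: "The interim analyses will examine the effect sizes of these two primary outcomes and observed statistical significance". Recruitment continues if a detectable effect is present but not yet significant, or if "Bayes Factors do not provide support for either the null or alternative hypothesis (BF10 > 0.3 and < 3"). In that case the plan is to "adjust p values (dividing by 2 for outcomes examined at interim to account for multiple analyses"), and the same sentence gives the reason: "to account for error rate inflation for final full sample analyses".

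The Protocol gives no reduced significance level, such as 0.025, and nowhere says that the threshold rather than the p value is halved. It states no separate significance level for the interim.

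**The concern.** A correction for repeated looks must make the final test harder to pass, either by lowering the threshold or by raising the p value. This rule lowers the p value and leaves the threshold alone, so the operation contradicts its stated purpose.

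Both primary outcomes fall under it. An analyst who follows the text would report halved p values as corrected for multiplicity when the false-positive rate of the final test had in fact doubled. An analyst who follows the evident intent would depart from a published rule, possibly after seeing the data. Any final p between 0.025 and 0.10 is significant on one reading and not on the other, which is the kind of choice that pre-specification is meant to remove.

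**Working it through.** **Inputs from the Protocol**
- Primary threshold: p<0.05 (Inference criteria). Sidedness is not stated; two-sided is assumed.
- Adjustment: the final p value is divided by 2 (Stopping rule).
- Looks at 224 and 450 participants (Stopping rule; 400 × 1.125 = 450 in Sample size). Information fraction 224/450 = 0.498.
- Stated power at N=400: 94% for PME and 88.5% for NPM (Sample size).

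**Step 1: the final test as written.** p/2 < 0.05 ⇔ p < 0.10. The critical value falls from |z| > 1.960 to |z| > 1.645, so the type I error of the final test is 0.10, not 0.05. Example: p = 0.08 becomes 0.08/2 = 0.04 and is declared significant. This step needs no modelling.

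**Step 2: both looks together.** The interim and final z statistics are taken as bivariate normal under the null, with correlation √(224/450) = 0.7055. Overall error = 1 − P(|Z1| < c1 and |Z2| < c2).

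| Interim p threshold | Final p threshold | Overall error per outcome |
|---|---|---|
| no positive claim possible | 0.10 (as written) | 10.0% |
| 0.006 | 0.10 | 10.2% |
| 0.019 | 0.10 | 10.7% |
| 0.05 | 0.10 | 12.5% |
| 0.05 | 0.05 (no correction) | 8.3% |
| 0.05 | 0.025 | 6.4% |
| 0.025 | 0.025 | 4.3% |
| 0.0294 | 0.0294 | 5.0% |

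The rows at 0.006 and 0.019 cover an early claim that needs both significance and BF10 > 3. The Protocol states no prior. For a two-sample t test with 112 per arm and an assumed Cauchy prior, BF10 = 3 corresponds to an interim p of 0.0186 at scale 0.2, 0.0146 at 0.5, 0.0116 at 0.707 and 0.0063 at 1.414. At p = 0.05, BF10 is only 0.5 to 1.6, which lies in the range where recruitment continues. The 12.5% row therefore applies only if p<0.05 alone were enough for an early claim.

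With 0.025 at the final look only, the overall error passes 5% once the interim threshold is looser than about 0.034.

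**Step 3: power under a corrected threshold.** Normal approximation from the stated powers: shift = 1.96 + z(power), which is 3.515 for PME and 3.160 for NPM at N=400. At N=450 multiply by √(450/400) = 1.061, giving 3.728 and 3.352. Power = Φ(shift − critical value), with critical value 2.241 for 0.025.

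| | PME at 0.05 | PME at 0.025 | NPM at 0.05 | NPM at 0.025 |
|---|---|---|---|---|
| N=400 | 94% | 90% | 88.5% | 82% |
| N=450 | 96% | 93% | 92% | 87% |

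**The case against.** The strongest reply is that this is loose shorthand. The sentence states its protective purpose twice and the rule cites a paper on sequential analysis, so a statistician would read it as halving the threshold to 0.025. The Analysis Plan also promises a full plan before any interim analysis, and the adjustment applies only if recruitment continues. All of this is fair, and the intent is not in doubt. But the words name p values as the thing divided, and nothing in the Protocol overrides them. A later plan would either inherit the error or contradict the Protocol. Continuing is also the route to the full sample of 450, where the main results are tested.

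A second reply is that stopping for futility lowers the error. If the BF10 < 0.3 stop were binding on each outcome's own data, the 10.2% to 10.7% would become about 8.0% at prior scale 0.5 and 6.5% at 0.707 (4.0% to 10.7% over scales 0.2 to 1.414). Little weight can be put on this, for two reasons:
- Read naturally, the stop requires that it be "extremely unlikely that either of the predicted effects would be observed up to maximum sample size capacity", that is, that neither effect looks attainable. A null NPM outcome is then unprotected whenever PME shows an effect.
- These figures treat participants as independent, although condition is assigned by day. If, for illustration, the stated ICC of 0.2 acts at day level with 20 people per day, the design effect is 1 + 19 × 0.2 = 4.8 and 224 people carry the information of about 47. The smallest attainable BF10 at scale 0.707 is then about 0.29, so the stop would almost never trigger and the error moves back towards 10%.

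A third reply, which stands, is that the power figures are only as good as the stated 94% and 88.5%. Simple design-effect formulas did not reproduce these (for NPM they gave about 4% to 10%). The losses in Step 3 are therefore conditional on the Protocol's own powers.

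**Conclusion.** The concern holds. As written, the final test of each primary outcome runs at 10% instead of 5%. That result depends only on the division by 2 and the p<0.05 criterion. Over both looks, without futility stopping, the error is 10.0% to 12.5%, assuming two-sided tests and information proportional to sample size; where in that range depends on an interim criterion the Protocol does not state. At the same interim level of 0.05, the written correction (12.5%) is worse than no correction (8.3%).

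It is probably a slip of wording, but it sits in the rule that decides both primary outcomes, so it must be corrected before the interim analysis. A change made afterwards would look driven by the data.

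**What to change.** In the Stopping rule, replace the division of p values with wording such as: *Each primary outcome is tested against a two-sided threshold of 0.025 (0.05/2), at the interim if a positive claim can be made there and at the final analysis; p values are not altered.* In the Inference criteria, add that once the interim has been done the primary outcomes use this threshold in place of p<0.05, with a reference to the Stopping rule.

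Using 0.025 at the interim as well keeps the overall error at no more than 4.3% per outcome, whatever Bayes-factor prior is chosen. A threshold of 0.0294 at both looks is a slightly less strict alternative that uses the full 5%.

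The cost is two sentences and some power. If the stated powers are right and information grows with N, power at N=450 falls from about 96% to 93% for PME and from about 92% to 87% for NPM. With 0.0294 it would be about 94% and 88%. Design, recruitment and data collection are unchanged.

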Appendix A: Recruitment text

This is a study exploring eating out at restaurants. If you wish to take part, you will need to complete a short screening questionnaire to ensure you are eligible to take part.

If you would like to take part, please make sure:

- You currently reside in Liverpool and can visit a restaurant in the city centre for lunch on a weekday.
- You regularly eat food prepared out of the home (from restaurants, cafes, fast food, etc.)
- You are over the age of 18 years
- You are a fluent English speaker
- You are **not** pregnant/breastfeeding
- You have **no** current or historic eating disorder

If you are eligible, you will be asked to come to a restaurant in Liverpool city centre for lunch at a pre-specified time between 12 and 2:30pm on a weekday. You can bring up to 4 friends with you to take part. All participants must meet the above criteria.

You will be able to choose a meal from a full restaurant menu and asked to complete a couple of short questionnaires. You will each pay for the meal yourself and receive monetary reimbursement of £20 for your time once the study is complete. This reimbursement should cover meal and travel costs associated with taking part in the study.

The following morning you will be sent a link to follow to report what you ate for the rest of the day following the meal.

To complete the screening questionnaire, please follow the link below:

[insert link]

Appendix D: Follow up questionnaire

1. How comfortable did you feel in this restaurant?

- □ Very uncomfortable
- □ Slightly uncomfortable
- Neutral
- Comfortable
- □ Very comfortable

2. Was this restaurant representative of restaurants you normally eat in?

- Yes
- □ No

3. Would you eat in this restaurant again?

- 🗆 Yes
- □ No
- Maybe

3a. Please elaborate on the reasons behind your answer to the previous question.

4. What do you think the aim of this study was?

5. Did you share any of the food or drink items?

- □ Yes
- □ No

5a. [if yes] What items were shared? Please give an estimation in % of how much of each item was shared and specify what was (i) given to others and (ii) received from others.

Example response: Potato bites, 20% given to others. Greek salad, 10% received from others.

6. Did you add any condiments (e.g., sauce, salt, pepper) to your food?

- □ Yes
- 🗆 No

6a. [if yes] What condiments did you add? Please give an estimation in teaspoons of how much of each condiment was added.

Example response: ½ teaspoon of salt

7. [Health food choice motives measure] Several different factors influence our choice of food. Read each item carefully and decide how important the item is to you. There are no right or wrong answers, we are interested in what is important to you.

It is important to me that the food I eat on a typical day...

		Not at all important 1	A little important 2	Moderately important 3	Very important 4
1	Is high in fibre and roughage	0	0	0	0
2	Is nutritious	0	0	0	0
	This is an attention check.	0	0	0	0
	Please select the answer (2) 'A little important'				
3	Contains a lot of vitamins and minerals	0	0	0	0
4	Is high in protein	0	0	0	0
5	Keeps me healthy	0	0	0	0
6	Is good for my skin/teeth/hair/nails etc.	0	0	0	0

8. This is an attention check. How many times have you visited the planet Mars?

- o Several times
- Just once
- o Never

9. What is your age (in years):

10. What is your sex? A question about gender identity will follow

- Male
- Female
- 11. Which of the following best describes your gender?
 - 🗆 Man

- Woman
- □ Non-binary
- Other
- Prefer not to say

12. What is your highest educational qualification? If you are a student please select the qualification being studied for.

- □ Less than high school
- □ High school completion
- □ College or foundation degree
- □ Bachelor's degree
- □ Master's degree
- □ Doctoral or professional degree
- 13. Please select your ethnicity:
 - □ White English/Welsh/Scottish/Northern Irish/British
 - White Irish
 - □ Any other White background
 - □ White and Black Caribbean
 - □ White and Black African
 - □ Any other mixed/multiple ethnic background please describe
 - Indian
 - Pakistani
 - Bangladeshi
 - □ Chinese
 - Other Asian
 - African
 - □ Caribbean
 - 🗆 Arab
 - □ Any other ethnic group
- 14. What is your weight
 - 🗆 In KG _____
 - In Stone and pounds _____
 - Prefer not to say

15. What is your height

- In centimetres_____
- In feet and inches _____
- Prefer not to say

[figure not shown]
16. How often, on average, over the past year have you eaten out (e.g., at a restaurant, café)?

- □ Not in the last year
- □ Less than once per month
- □ 1-3 times per month
- □ 1-2 times per week
- □ 3 times per week or more

17. Did you notice a label on the food menu? [If no, skip to Q21]

- 🗆 Yes
- 🗆 No

18. Which labels/information did you see on the food menu? (select one of the following) [If incorrect, skip to Q21]

19. Did the label/information influence your food selection? (Yes/No) [If no, skip to Q21]

Yes

🗆 No

[figure not shown]
20. How did the label/information influence your food selection?

- a. I chose a meal with a healthier classification
- b. I avoided a meal with a less healthy classification
- c. Other

21. Nutri-score is a labelling strategy used in several European countries on food packaging. Nutri-score represents the healthiness of menu items on a scale of A (healthiest) to E (least healthy). This score is calculated according to the amount of healthy and unhealthy nutrients.

If the UK government introduced a policy requiring the use of a 'Nutri-score' system on food menus, how would you feel? (Likert scale ranging from 1-5 anchored by "strongly oppose" and "strongly support")

22. [PME measure - participants in both conditions (calorie labels/NS with calorie labels) will be given the menu they ordered from].

Please look at the menu you were given, and think about the menu.

"The menu made me concerned about the health effects of consuming less healthy menu items"

- □ Strongly disagree
- □ Slightly disagree
- □ Neither agree nor disagree
- □ Slightly agree
- □ Strongly agree

"The menu made consuming less healthy items seem unpleasant"

- □ Strongly disagree
- Slightly disagree
- □ Neither agree nor disagree
- □ Slightly agree
- □ Strongly agree

"The menu discouraged me from wanting to consume less healthy items".

- □ Strongly disagree
- □ Slightly disagree
- □ Neither agree nor disagree
- □ Slightly agree
- □ Strongly agree

